18.1 Definition of Baseline

The Baseline I value will be defined as the value captured either at the Screening Visit or the Baseline Visit of the lead-in study, whichever comes later.

Unless otherwise specified, the Baseline II Visit is the same as the Completion Visit (Visit 7/Week 24) in the lead-in studies (14861A and 14862A).

LU Study Number: 14861B Trial Site Number: Study Level Pluto ID: CLI 00933680

Baseline III is the same as the Completion Visit (Visit 6/Week 28) of the open-label treatment period.

18.2 Derived Variables

18.2.1 MMSE Total Score and MMSE Stratum

MMSE consists of 8 subcategories (orientation to time, orientation to place, registration, attention and calculation, recall, language, repetition, and complex commands), with in total 30 questions recording correct/incorrect responses (coded 1/0). The MMSE total score is defined as the sum of the 30 questions and the total score ranges from 0 to 30 (at screening 12 to 22 due to inclusion criterion), with a lower scores meaning more severe dementia.

The subcategory *attention and calculation* consists of 5 questions (aCRF items MMSE04A to MMSE04E), where the patient continuously should subtract 7 from 100 (correct responses 93, 86, 79, 72, and 65). If a question is answered incorrectly and the subsequent questions not are recorded, the missing responses will be counted as incorrect (0).

The total score will be missing if three or more items scores are missing, and if less than three item scores are missing the missing item scores will be imputed by the worst case (0).

MMSE stratum (mild, MMSE total score ≥19; moderate, MMSE total score <19) used in the analyses will be based on the assessment collected at the lead-in study screening visit.

18.2.2 ADAS-Cog Total Score

The ADAS-Cog assess the patient's orientation, memory (word recall, recognition, and remembering instructions), language (spoken language ability, comprehension of the spoken language, word finding difficulty, naming objects and fingers, following commands), and praxis (ideational and constructional). The ADAS-Cog total score is defined as the sum of the 11 item scores described in Panel 7. If three or more items scores are missing, the total score will be missing. If less than three item scores are missing item scores will be imputed by the worst score for the item.

The ADAS-Cog total score ranges from 0 to 70, with a lower score indicating a lower cognitive impairment.

LU Study Number: 14861B Trial Site Number: Study Level Pluto ID: CLI 00933680

Panel 7 Definition of ADAS-Cog Item Scores

ADAS-Cog Item	Data collected in the eCRF (aCRF variable name)	Defintion of ADAS-Cog Item Scores used in the calculation of the total score (SADs paramed name)
1. Word recall task	Total number of word recalled correctly, recorded in three trials (ranges 0-10 in each trial): ADCOG01 ADCOG02 ADCOG03	Average of the total number of words recorded incorrectly in the three trials rounded to the closest integer with .5 rounded upwards (ranges from 0-10): ACITM01=round(((10- ADCOG01)+(10- ADCOG02)+(10- ADCOG03))/3,1.); If <3 of the eCRF scores are missing, the item score will be the average of the
2. Naming task	Total number of object/fingers named correctly (ranges 0-17) ADCOG05	available scores. eCRF score converted to total number of object/fingers named incorrectly (17-ADCOG05), and then classified according to the scoring scheme below (ranges 0-5): ACITM02= 0 = 0 - 2 1 = 3 - 5 2 = 6 - 8 3 = 9 - 11 4 = 12 - 14 5 = 15 - 17
3. Commands	Total number of commands performed correctly (ranges 0-5): ADCOG07	eCRF score converted to total number of commands_performed incorrectly (ranges 0-5): ACITM03=5- ADCOG07;
4. Constructional praxis	Total number of drawings performed incorrectly (ranges 0-5): ADCOG08	ACITM04= ADCOG08
5. Ideational praxis	Total number of steps completed correctly (ranges 0-5): ADCOG09	eCRF score converted to total number of steps completed incorrectly (ranges 0-5): ACITM05=5- ADCOG09;
6. Orientation	Total number of items answered correctly (ranges 0-8): ADCOG10	eCRF score converted to total number of items answered incorrectly (ranges 0-8): ACITM06=8- ADCOG10;
7. Word recognition task	Total number of words identified correctly and total number of words identified incorrectly (both scores ranges 0-12):	Total number of words identified incorrectly, where scores>12 truncated to 12 (ranges 0-12):

LU Study Number: 14861B Pluto ID: CLI_00933680

Status: Final

Trial Site Number: Study Level

Version: 1.0

		A CITY 107
	ADCOG11	ACITM07= Min((12, ADCOG11)+ ADCOG12, 12):
	ADCOG11	Min((12- ADCOG11)+ ADCOG12, 12);
	ADCOG12	If ADCRGT01 or ADCRGT02 is missing,
		the item score will be missing
8. Remembering test instructions	Level of impairment (ranges 0-5,	ACITM08= ADCOG14
8	see category labels below):	
	ADCOG14	
	0 = None	
	1 = Very Mild 2 = Mild	
	3 = Moderate	
	4 = Moderately Severe	
	5 = Severe	
9. Language	Level of impairment (ranges 0-5, same category labels as for item 8):	ACITM09= ADCOG15
	ADCOG15	
10. Comprehension of spoken language	Level of impairment (ranges 0-5, same category labels as for item 8):	ACITM10= ADCOG16
	ADCOG16	
11. Word finding difficulty	Level of impairment (ranges 0-5, same category labels as for item 8):	ACITM11= ADCOG17
	ADCOG17	

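### Read literally, the SAP's missing-trial rule for ADAS-Cog word recall averages words correct, without the reversal and rounding that the item's definition requires; the wording needs correcting

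*SAP*

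**What the plan says.** All of this is in SAP 18.2.2 (ADAS-Cog Total Score), mainly Panel 7.

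- **What is collected for item 1 (ADCOG01 to ADCOG03):** "Total number of word recalled correctly, recorded in three trials (ranges 0-10 in each trial".
- **How the item is defined:** "Average of the total number of words recorded incorrectly in the three trials rounded to the closest integer with .5 rounded upwards".
- **The printed formula (closing characters omitted here):** "ACITM01=round(((10- ADCOG01)+(10- ADCOG02)+(10- ADCOG03))/3,1". Each trial is subtracted from 10 before averaging.
- **The missing-trial rule, directly after the formula:** "If <3 of the eCRF scores are missing, the item score will be the average of the" "available scores". The extracted text breaks between these two pieces. That comes from the PDF and is not a fault in the plan.
- **How Panel 7 uses the term elsewhere:** for item 3, "eCRF score converted to total number of commands_performed incorrectly (ranges 0-5". Items 2, 5 and 6 follow the same pattern, so in those rows the eCRF score is the raw value and the conversion is stated.
- **Direction and range of the total:** "The ADAS-Cog total score ranges from 0 to 70, with a lower score indicating a lower cognitive impairment".

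SAP 18.2.2 also says that if fewer than three item scores are missing, each missing item takes its worst score. SAP section 3 lists change in ADAS-Cog total from Baseline I and from Baseline II as the first two secondary efficacy endpoints. SAP 10.2 analyses change from Baseline I by MMRM, using lead-in and extension visits together.

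**The concern.** The only antecedent of the available scores in the missing-trial sentence is the eCRF scores, and for item 1 those are words correct. The sentence mentions neither reversal nor rounding. The formula above it does not fill the gap: it adds the three reversed trials with plus signs, and in SAS, the software named in SAP section 16, such a sum is missing when any term is missing. For a record with one or two missing trials, this sentence is therefore the only rule available to the programmer.

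The literal result also clashes with the SAP's handling of missing items. A patient with two trials scored 0 and the third missing would get item score 0, the best possible. A patient with all three trials missing would have a missing item and, if fewer than three items were missing, would be given the worst score, 10.

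At stake is the correctness of one item, worth 10 of 70 points, on the affected records. Those records feed the ADAS-Cog summaries and the MMRM.

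**Working it through.** **1. Reproduce the plan's own range.** The item maxima in Panel 7 sum to 10 + 5 + 5 + 5 + 5 + 8 + 12 + 5 + 5 + 5 + 5 = 70, which matches the stated 0 to 70. The complete-data formula gives 10 for trials (0, 0, 0), 0 for (10, 10, 10) and 6 for (3, 4, 5). The definition and formula agree with each other and with the direction of the total.

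**2. Compare the two readings when a trial is missing.** Let m be the mean number of words correct over the available trials.

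- As written: item = m.
- By the item's definition: item = 10 − m, then rounded with .5 upwards.
- Difference before rounding: m − (10 − m) = 2m − 10.

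| Available trials | As written (m) | 10 − m | By definition, rounded | 2m − 10 |
|---|---|---|---|---|
| 0, 0 | 0 | 10 | 10 | −10 |
| 2, 3 | 2.5 | 7.5 | 8 | −5 |
| 3, 4 | 3.5 | 6.5 | 7 | −3 |
| 5, 5 | 5 | 5 | 5 | 0 |
| 6, 7 | 6.5 | 3.5 | 4 | +3 |
| 8, 8 | 8 | 2 | 2 | +6 |
| 10, 10 | 10 | 0 | 0 | +10 |
| 3 only | 3 | 7 | 7 | −4 |
| 7 only | 7 | 3 | 3 | +4 |

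The missing rounding matters separately. For (3, 4), even a programmer who reverses could record 6.5 or 7.

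**3. Direction.** The sign of 2m − 10 depends only on whether m is below or above 5. With two trials available there are 11 × 11 = 121 score pairs: the literal score is too low in 55, equal in 11 and too high in 55. With one trial available the counts are 5, 1 and 5 out of 11. These count possible scores and are not patient frequencies.

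**4. Complete records.** Fewer than three missing also includes none missing. Applied there, with rounding, the literal sentence disagrees with the printed formula in 1060 of the 11 × 11 × 11 = 1331 possible score triples.

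**5. Effect on change from baseline.** Take a patient with available trials 2 and 3, so that item 1 is 5 points too low before rounding. If this happens at a follow-up visit, worsening from Baseline I is understated by 5. If it happens at Baseline I, worsening is overstated by 5.

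**6. Bound on a mean.** If a proportion p of assessments is affected, the mean ADAS-Cog total at a visit moves by at most 10p points. The documents give no value for p. Purely as an assumption, p from 0.5% to 2% gives at most 0.005 × 10 = 0.05 to 0.02 × 10 = 0.2 points on the 70-point scale. That bound requires every affected record to have the largest error in the same direction.

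**The case against.** The strongest reply is that the literal reading is not what the authors meant. The sentence stands in the cell that defines the item as words incorrect, directly after a formula that reverses each trial, and reads naturally as the same average over fewer trials. Step 4 supports this: taken literally, the sentence would overrule the formula for complete data, which cannot be intended. This stands as evidence of intent. It does not change what the sentence says, and it leaves rounding unstated and complete records wrongly covered.

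A reader might infer three stronger claims that the documents do not support:

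- **That the item is scored backwards.** The documents show a defective sentence. They do not show how the derivation was programmed.
- **That impaired patients look better, so decline is understated.** The error reverses above 5 words, and an error at Baseline I overstates decline. Nothing shows that impaired patients miss trials more often: a patient who recalls nothing can be recorded as 0, which is within the collected range.
- **That the ADAS-Cog results are materially affected.** The frequency of missing trials is not given. The primary objective is safety and tolerability. Protocol 16.8 and SAP 10.2 make the efficacy modelling exploratory, and SAP 10.1 presents nominal p-values.

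**Conclusion.** The point holds as a drafting defect and is minor. The missing-trial sentence, followed as written, contradicts the item's own definition and formula and can put item 1 wrong by anything from −10 to +10 points on an affected assessment. The reversed reading is very probably the intended one.

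The size rests on two conditions that the documents do not settle: that the sentence is programmed literally, and that some assessments have one or two of the three trials missing. If the code already averages reversed scores and rounds them, no result changes and only the text needs correcting. No overall direction of bias in change from baseline can be stated.

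**What to change.** Replace the sentence in Panel 7, item 1 with: *If one or two of the three trial scores are missing, the item score is the mean of (10 − eCRF score) over the available trials, rounded to the nearest integer with halves rounded up; if all three are missing, the item score is missing.* This restores the reversal and rounding, limits the rule to incomplete records, and leaves the worst-score rule to handle a fully missing item.

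Then confirm that the derivation code does this at every visit entering the MMRM. The lead-in derivation is not in these documents, so agreement between lead-in and extension scores has to be checked and cannot be assumed. In the same pass, correct the missing-data note for item 7, which names ADCRGT01 and ADCRGT02 although that row collects ADCOG11 and ADCOG12.

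The cost is one sentence, at most one line of code, and the lead-in check. Scores from complete records, as given by the printed formula, do not change.

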18.2.3 ADCS-ADL₂₃ Total Score

The ADCS-ADL₂₃ scale contains of 23 item scores (See Panel 8), where each item contains one or more questions.

The ADCS-ADL₂₃ total score is defined as the sum of the 23 item scores. "Don't know" responses will be counted as worst case (0). For patients institutionalized, item score number 18 (Left On His/Her Own) will be counted as worst case (0). The scoring scheme for the item scores are described in Panel 8.

Trial Site Number: Study Level

LU Study Number: 14861B Pluto ID: CLI 00933680

Panel 8 ADCS-ADL₂₃ Items

ADCS-ADL ₂₃ Item	Data collected in the eCRF (aCRF variable name)	Defintion of ADCS-ADL ₂₃ Item Scores used in the calculation of the total score (SADs paramed name)
1. Usual Eating Performance	ADADL01	Item score ranges 0-3:
		ADL01=ADADL01
2. Optimal Walking Performance	ADADL02	Item score ranges 0-3:
2 II 1 D 1/D1 11	1.0.1.0.1.0.2	ADL02=ADADL02
3. Usual Bowel/Bladder Function	ADADL03	Item score ranges 0-3:
		ADL03=ADADL03
4. Usual Bathing Performance	ADADL04	Item score ranges 0-3:
		ADL04=ADADL04
5. Optimal Grooming Performance	ADADL05	Item score ranges 0-3:
		ADL05=ADADL05
6. Dressing	ADADL06	Item score ranges 0-7:
	ADADL07	If ADADL06="No" or ADADL06="Don't know" then
	ADADL08	ADL06=0;
		else if ADADL06="Yes" then ADL06=
		ADADL07;
5 T	1.0.1.0.0	ADL06=ADL06+ADADL08;
7. Use a Telephone	ADADL09	Item score ranges 0-5:
	ADADL10	If ADADL09="No" or
		ADADL09="Don't know" then
		ADL07=0; else if ADADL09="Yes" then ADL07=
		ADADL10;
8. Watch Television	ADADL11	Item score ranges 0-3:
	ADADL12	if ADADL11="No" or
	A D A D L 12	ADADL11="Don't know" then
	ADADL13	ADL08=0; %**"Yes"/"No"/"Don't know" counted
	ADADL14	as 1/0/0;
		else if ADADL11="Yes" then
		ADL08= ADADL12+ADADL13+
		ADADL14;

LU Study Number: 14861B Pluto ID: CLI_00933680

Status: Final

Trial Site Number: Study Level

Version: 1.0

9. Pay Attention to Conversation	ADADL15	Item score ranges 0-3:
	ADADL16	If ADADL15="No" or ADADL15"Don't know" then ADL09=0; else if ADADL15="Yes" then ADL09= ADADL16;
10. Clear Dishes	ADADL17	Item score ranges 0-3:
	ADADL18	If ADADL17="No" or ADADL17="Don't know" then ADL10=0; else if ADADL17="Yes" then ADL10= ADADL18;
11. Find Belongings	ADADL19	Item score ranges 0-3:
	ADADL20	If ADADL19="No" or ADADL19="Don't know" then ADL11=0; else if ADADL19="Yes" then ADL11= ADADL20;
12. Obtain Beverage	ADADL21	Item score ranges 0-3:
	ADADL22	If ADADL21="No" or ADADL21="Don't know" then ADL12=0; else if ADADL21="Yes" then ADL12= ADADL22;
13. Make a Meal	ADADL23	Item score ranges 0-4:
	ADADL24	If ADADL23="No" or ADADL23="Don't know" then ADL13=0; else if ADADL23="Yes" then ADL13= ADADL24;
14. Dispose of Garbage	ADADL25	Item score ranges 0-3:
	ADADL26	If ADADL25="No" or ADADL25="Don't know" then TADL14=0; else if ADADL25="Yes" then ADL14= ADADL26;
15. Get Around Outside Home	ADADL27	Item score ranges 0-4:
	ADADL28	If ADADL27="No" or ADADL27="Don't know" then ADL15=0; else if ADADL27="Yes" then ADL15= ADADL28;

Trial Site Number: Study Level

16.0.01	1 D 1 D1 20	Tr. O.4
16. Go Shopping	ADADL29	Item score ranges 0-4:
	ADADL30	If ADADL29="No" or ADADL29="Don't know" then
	ADADL31	ADL16=0; %**"Yes"/"No"/"Don't know" counted
		as 1/0/0 (ADADL31);
		else if ADADL29="Yes" then ADL16= ADADL30+ ADADL31;
17. Keep Appointments	ADADL32	Item score ranges 0-3:
17. Heep rippointments		
	ADADL33	If ADADL32="No" or ADADL32="Don't know" then
		ADL17=0;
		else if ADADL32="Yes" then ADL17=
18. Left On His/Her Own	ADADL34	ADADL33;
18. Left On His/Her Own	ADADL34	Item score ranges 0-3:
	ADADL35	If ADADL34="Checked" then ADL18=0;
	ADADL36	else if ADADL35="No" or ADADL35="Don't know" then
		ADL18=0;
	ADADL37	%**"Yes"/"No"/"Don't know" counted
	ADADL38	as 1/0/0; else if ADADL35="Yes" then
		ADL18= ADADL36+ ADADL37+
10 7 11 11 0	1.5.15.40	ADADL38;
19. Talk About Current Events	ADADL39	Item score ranges 0-3:
	ADADL40	if ADADL39="No" or
	ADADL41	ADADL39="Don't know" then ADL19=0;
	TIDINDE TI	%**"Yes"/"No"/"Don't know" counted
	ADADL42	as 1/0/0;
		else if ADADL39="Yes" then ADL19= ADADL40+ ADADL41+
		ADADL42;
20. Read More Than 5 Minutes	ADADL43	Item score ranges 0-2:
	ADADL44	if ADADL43="No" or
	ADADL45	ADADL43="Don't know" then ADL20=0;
	ADADL I J	%**"Yes"/"No"/"Don't know" counted
		as 1/0/0;
		else if ADADL43="Yes" then ADL20= ADADL44+ ADADL45;
21. Write Things Down	ADADL46	Item score ranges 0-3:
	ADADL47	If ADADL46="No" or
		ADADL46="Don't know" then
		ADL21=0; else if ADADL46="Yes" then ADL21=
		ADADL47;
	l	,

22. Perform Pastime	ADADL48	Item score ranges 0-3:
	ADADL49	If ADADL48="No" or ADADL48="Don't know" then ADL22=0; else if ADADL48="Yes" then ADL22= ADADL49;
23. Use Household Appliance	ADADL50	Item score ranges 0-4:
	ADADL51	If ADADL50="No" or ADADL50="Don't know" then ADL23=0; else if ADADL50="Yes" then ADL23= ADADL51;

If five or more items scores are missing, the total score will be missing. If less than five item scores are missing, the missing questions within the item score will be imputed by the worst case for each missing question (missing main responses will be imputed by 0; if the main response equal to "Yes", missing subsequent question(s) will be imputed by the worst score for each question).

The ADCS-ADL₂₃ total score ranges from 0 to 78, with a higher score indicating a higher functioning status.

18.2.4 NPI Total Score and Individual Items

The NPI scale consists of 12 domains (Delutions, Hallucinations, Agitation/Aggression, Depression/Dysphoria, Anxiety, Elation/Euphoria, Apathy/Indifference, Disinhibition, Irritability/Lability, Aberrant Motor Behaviour, Sleep, and Appetite and Eating Disorders). The NPI total score is defined as the sum of the 12 domain scores, where the domain score for each domain is calculated as (the domain is given by category 1-12 in the aCRF variable NPI01):

- If status (aCRF NPI02) is equal to "Not Applicable" or "No", the NPI domain score will be equal to 0; otherwise, the NPI domain score will be the product of frequency (aCRF NPI03, ranging from 1 to 4), and severity (aCRF NPI04, ranging from 1 to 3).
- If four or more domain scores are missing (due to missing record in status, or missing frequency, or severity for the domain), the NPI total score will be missing. If less than four domain scores are missing, the missing doimains will in the calculation of the NPI total score be imputed by the mean of the non-missing domain scores, rounded to the closest integer (.5 rounded upwards).

Each domain score ranges from 0 to 12, and the NPI total score ranges from 0 to 144 with a higher score indicates a more serious behavioral issue.

LU Study Number: 14861B Trial Site Number: Study Level Pluto ID: CLI 00933680

Page 32 of 48

18.3 **Assigning Data to Visits**

18.3.1 **Rating Scales**

The assessment at the Withdrawal Visit for patients withdrawn from treatment will be assigned to a nominal visit in the Treatment Period, according to the visit windowing specified in Panel 9 and Panel 10. The assessment collected at the scheduled visit will be used in the analyses, or the windowed assessment from the Withdrawal Visit if no schedule assessment is available. If the assessment at the Withdrawal Visit is assigned to the same visit as an assessment at a scheduled visit, the assessment from the scheduled visit will be used. Otherwise, the assessments at the scheduled visits will be used.

Panel 9 **Visit Windows for Efficacy Assessments (open-label treatment period)**

Nominal Visit Number	Nominal Visit Week	Nominal Visit Day	Time Window
V1 (Baseline II /Completion Visit for lead-in study)	0	0	0
V4	12	84	1 to 139
V6 (Completion/Withdrawal)	28	196	>139

MMSE is only assessed at Baseline II, Baseline III and the Completion/Withdrawal visit. As such, the visit windows for MMSE are specified in Panel 10.

Panel 10 Visit Windows for MMSE

Nominal Visit Number	Nominal Visit Week	Nominal Visit Day	Time Window
V1 (Baseline II /Completion Visit for leadin study)	0	0	0
V6 (Baseline III/Completion Visit for open- label treatment period)	28	196	1 to 279
V11 (Completion Visit for open-label treatment period with memantine)	52	364	>279

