9.2.3 Dependence scale

The Dependence scale¹⁵ is a clinician-rated scale designed to measure dependence as a health outcome measure in Alzheimer's disease. The Dependence scale is a 13-item scale with questions on social and occupational functioning. Two questions are rated by frequency (*No*, *Occasionally, Frequently*) and the remaining questions have yes or no responses. The answers are used to derive a dependence level from 0 (*no dependence*) to 5 (*complete dependence*). The clinician interviews an informant who lives with or is well-informed about the patient's day to-day activities. The Dependence scale can be rated by a clinician after a short training session. It takes approximately 15 minutes to complete the scale.

In this study the informant will be the patient's caregiver.

The Dependence scale should be completed following the ADCS-ADL by the same rater.

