10.2 Exploratory Analysis of Efficacy

Changes from baseline I in ADAS-Cog total score, ADCS-ADL₂₃ total score, NPI total score, NPI individual items, and MMSE total score will be analysed using a restricted maximum likelihood (REML)-based mixed model for repeated measures (MMRM) approach. Baseline will be defined as the baseline in the lead-in study (Baseline I). The model will include data from visits in both the lead-in study and the open label treatment period. The model will include the fixed categorical effects of treatment group in the lead-in study, country, visit week, treatment-by-week interaction, MMSE-stratum ($<19, \ge19$) at baseline I, and MMSE-stratum at baseline I-by-visit interaction and the continuous covariates of baseline score and baseline score-by-visit interaction.

In all analyses, an unstructured covariance structure will be used to model the within-patient errors. The Kenward-Roger approximation will be used to estimate denominator degrees of freedom. The analysis will be based on the missing-at-random (MAR) assumption and performed using all available observations (observed cases [OC] data).

Line plots will be created to illustrate the MMRM estimates of least squares means by visit week. ADCS-CGIC will be analysed using the same methodology, using the scores at each visit and the ADCS-CGIC score at Baseline I in the lead-in study as baseline.

LU Study Number: 14861B Trial Site Number: Study Level Pluto ID: CLI 00933680

11 Safety

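### As the flow charts read, SAP Panel 9 creates an extension Week 12 level for ADCS-ADL23 that holds only withdrawn patients

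*SAP*

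**What the plan says.** **Windowing.** SAP 18.3.1 states that Withdrawal Visit ratings "will be assigned to a nominal visit in the Treatment Period, according to the visit windowing specified in Panel 9 and Panel 10". The scheduled rating is used in the analyses, "or the windowed assessment from the Withdrawal Visit if no schedule assessment is available". Panel 9 covers the open-label efficacy assessments without naming scales. Its Visit 4 row reads "V4 12 84 1 to 139" (visit, week, nominal day, window); anything after day 139 goes to Visit 6.

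**The one exemption.** MMSE gets its own Panel 10, with no Visit 4 row, on the ground that "MMSE is only assessed at Baseline II, Baseline III and the Completion/Withdrawal visit".

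**Schedule.** In Protocol Panel 2 and in SAP Appendix II, the ADCS-ADL23 row is marked at Baseline II and at Visit 6 (Completion/Withdrawal), with Visit 4 blank. In the SAP chart, ADAS-Cog, ADCS-CGIC, NPI and the Dependence scale all carry a Visit 4 mark.

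**Use of the data.** SAP 10.1 summarises efficacy variables by visit week. SAP 10.2 fits an observed-case MMRM, under missing at random, to "Changes from baseline I in ADAS-Cog total score, ADCS-ADL₂₃ total score, NPI total score, NPI individual items, and MMSE total score". It uses lead-in and extension visits, states that "an unstructured covariance structure will be used to model the within-patient errors", and plots least-squares means by visit week.

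**The concern.** The reason given for taking MMSE out of Panel 9 applies equally to ADCS-ADL23 on the flow charts, but ADCS-ADL23 was left in. A withdrawal score from, say, day 60 would be filed at extension Week 12 (study Week 36), where no continuing patient is rated.

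For a scale that is scheduled at Visit 4, the window adds a few withdrawal values to a level dominated by continuing patients. For ADCS-ADL23 it would create a level with no continuing patients at all. Two outputs are exposed:

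- The Week 12 row of the by-visit summary would describe early withdrawals while looking like a cohort mean.
- The Week 12 least-squares mean would take its visit effect, and its treatment, stratum and baseline interactions with visit, from early withdrawals alone, then project them onto everyone. Missing at random is doubtful there, because every continuing patient is unobserved by design.

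There is also an estimation issue: one element of the covariance matrix would have no data behind it.

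**Working it through.** **1. The plan's own figure.** SAP section 15 and Protocol 16.11 give (3×310 + 3×280) × 85% × 85% ≈ 1280 completers.

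- 3×310 + 3×280 = 1770
- 1770 × 0.85 = 1504.5 lead-in completers
- 1504.5 × 0.85 = 1278.8, which reproduces the stated 1280
- 1504.5 − 1278.8 = 225.7 planned non-completers. This figure combines patients who are ineligible or do not enter with patients who enter and withdraw; the documents do not split it.

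**2. Which patients have an ADCS-ADL23 value at each level** (flow charts plus Panel 9 as written).

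| Patient | Extension Week 12 | Extension Week 28 |
|---|---|---|
| Completes | none scheduled | Visit 6 rating |
| Withdraws, rated day 1–139 | withdrawal rating | none |
| Withdraws, rated after day 139 | none | withdrawal rating |

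Completers at Week 12: 0. Patients with both values: 0. This needs no assumption about rates or timing.

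**3. How many records.** Neither the share of the 225.7 who enter and then withdraw nor the timing is given. Assume a share s, withdrawal uniform over 196 days, and every withdrawn patient rated. Then the Week 12 count is 225.7 × s × 139/196, and the Week 28 count is 1278.8 + 225.7 × s minus that.

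| s | Withdraw after entry | Week 12 records | Per lead-in study arm (÷6) | Week 28 records |
|---|---|---|---|---|
| 0.25 | 56 | 40 | 6.7 | 1295 |
| 0.50 | 113 | 80 | 13.3 | 1312 |
| 0.75 | 169 | 120 | 20.0 | 1328 |
| 1.00 | 226 | 160 | 26.7 | 1344 |

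**4. The covariance element.** With a REML fit, each patient enters the likelihood only through the block of the covariance matrix for the visits at which that patient has data. The Week 12/Week 28 element appears in a patient's block only if both values exist. By step 2 that is nobody, so the likelihood is exactly flat in that element. A zero row in the Hessian follows, which may surface as a non-positive-definite Hessian or other fitting warnings, including in the Kenward-Roger step.

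**5. What this does to Week 28.** Treatment, MMSE stratum and baseline score all interact with visit in the SAP 10.2 model, so the Week 12 values of withdrawn patients carry very little information about the Week 28 mean. A flat likelihood in one covariance element does not by itself move that mean.

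**The case against.** **The premise is a blank cell, and the charts as read have lost marks.** Adverse events at Visit 2 are blank in both charts, although Protocol 9.4.1 requires the question at each visit. IMP dispensing at Visit 10 is blank in both substudy charts, although Protocol 6.1 dispenses three wallet cards then. The ADCS-CGIC row of Protocol Panel 2 lacks the Visit 4 and Visit 6 marks that the SAP chart has. Two charts agreeing on a blank is therefore weaker support than it looks. This stands, and it is why the point is conditional on the schedule.

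**Some of the prose hints at a Visit 4 rating.** Exempting only MMSE suggests that the authors thought every other scale was rated at Visit 4. Protocol 9.2.3 adds: "The Dependence scale should be completed following the ADCS-ADL by the same rater", and the Dependence scale is marked at Visit 4. This is not decisive, because the substudy schedules the Dependence scale without any ADCS-ADL23. Against it, the ADCS-ADL23 row keeps its Visit 6 mark and lacks Visit 4 in both documents, and the SAP chart preserves Visit 4 for ADAS-Cog, ADCS-CGIC and NPI. A genuine gap is the better reading, but not a certain one.

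**The counts may be smaller.** Protocol 8.4 asks for a Withdrawal Visit only where possible, so some early withdrawals will leave no score. This stands.

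**The size of any distortion is unknown.** A simulation that assumed withdrawn patients were 4 points worse gave a Week 12 least-squares mean of −8.4 against a true −4.5. The 3.9-point gap largely returns the assumption, so it should not be read as an estimate.

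**Conclusion.** The point holds in conditional form. If ADCS-ADL23 is not rated at Visit 4, as both flow charts read, Panel 9 yields an extension Week 12 level made up wholly of withdrawn patients, and an unstructured covariance with one element that the data cannot inform. The number of records is about 160 over both lead-in studies if all planned non-completers entered and withdrew uniformly, and about 40 if a quarter did. Timing weighted to the early weeks would raise these counts, and missed Withdrawal Visits would lower them.

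A reader might infer that the study Week 52 (extension Week 28) ADCS-ADL23 estimate is biased or cannot be obtained. The documents do not support that: the identified risk is warnings or difficulty in fitting, and neither non-convergence nor a shift in the Week 28 estimate has been shown. Nor do the documents give any basis for stating how far the Week 12 mean would be off.

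The effect is confined to one interim point of one scale in an exploratory analysis. The primary safety objective is unaffected. It is worth correcting because a stated rule would produce a misleading row and plot point, and the correction is small.

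**What to change.** First, confirm the ADCS-ADL23 schedule against the original tables.

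- **If it is not rated at Visit 4:** add a window panel for ADCS-ADL23 with no Week 12 level. Withdrawal values from day 140 on go to Visit 6. Earlier values are listed and summarised separately as *withdrawal before day 140*, outside the by-visit table and the MMRM.
- **If it is rated at Visit 4:** correct both flow charts and leave Panel 9 as it stands.

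The cost is one short panel in the SAP or one corrected row in each chart. The downside of the first option is that early-withdrawal scores leave the MMRM, which sits awkwardly with the SAP 10.2 intention to use all available observations. An alternative is to map them to Visit 6, as Panel 10 does for MMSE. That keeps the values in the model but mixes ratings from the first weeks with ratings at Week 28. Either choice removes the withdrawal-only level and the empty covariance element; the SAP should say which is used.
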